3.1. Overall Study Design and Plan

This is a multicenter, randomized, double-blind, parallel, placebo-controlled, proof-of-concept, adaptive design, Phase 2 study to evaluate LB1148 for return of GI function, reduction of POI and intra-abdominal adhesions in subjects undergoing elective bowel resection with a planned stoma.

Figure 1 Illustration of Study Design for Protocol LBS-POI-201

* Study Day 0 is the day of surgery. Study dosing could occur on Day -1 and/or up to 2 hours prior to surgery on Day 0.

Subjects scheduled for elective bowel resection, aged 18 to 80 years inclusive, will be screened within 42 days of randomization (Study Day -1). Subjects who meet all inclusion and no exclusion criteria, and provide written informed consent, will be stratified by: 1) surgical approach (either minimally invasive technique or laparotomy) and 2) with or without a planned stoma, and then randomized to receive a split oral liquid dose of LB1148 or placebo (polyethylene glycol [PEG], glucose, and electrolytes) in a 1:1 ratio.

All subjects will receive 350 mL of study drug 6-10 and 2-6 hours prior to surgery (Study Day 1/2). Subjects will then undergo the first surgery. At the time of surgical closure, the investigator will determine the incidence, extent, and severity of adhesions using the Intra-Abdominal Adhesion Extent and Severity Assessment Worksheet ([Appendix 5](#)).

Subjects will be assessed for safety and tolerability, including AEs, physical exam, vital signs, clinical lab tests (chemistry, coagulation, and hematology) while in the hospital and on Day 30. Subjects will be monitored for return of bowel function while in the hospital and discharged following tolerance of solid food and first bowel movement.

Within 8 months of enrollment, subjects will undergo a second surgery for the purpose of ostomy take down or other planned abdominal surgery, at which time the surgeon will determine the incidence, extent, and severity of adhesions. If a subject is not ready for the second surgery by 8 months, the investigator may consult with Medical Monitor to obtain window approval.

Unless required for safety reasons or protocol compliance, all subjects, Investigators, and study site personnel will remain blinded to the identity of the treatment from time of randomization until final database lock.

The Schedule of Assessments is provided in [Appendix 1](#) and the study endpoints are in [Section 2.2](#).

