3.3. Study Duration and Dates

The total duration for subject participation is up to 10 months (screen through second surgery).

STUDY POPULATION SELECTION

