6.16. Adhesions Assessment (Day 0 and at time of second surgery)

The surgeon will determine the incidence, extent, and severity of adhesions at the time of surgical closure for the first surgery and at the time of opening for the second surgery. Grading of the adhesions (extent and severity) will be performed by the surgeon during the surgical procedure ([Appendix 5](#)).

For each abdominal region, the score of the extent and severity of adhesions are evaluated. The surgeon will grade the intra-abdominal adhesions at 9 abdominal region (right upper, epigastrium, left upper, left flank, left lower, pelvis, right lower, right flank and central) and when appropriate at 4 areas around the ostomy (superior, lateral, inferior, and medial). ([Coccolini et al., 2013](#), [Dabrowski et al., 2016](#), and the [Seprafilm Package Insert](#)).

For each abdominal region, extent of adhesion formation is scored for adhesions from the abdominal wall to bowel (including abdominal wall to viscera) and for adhesions from bowel to bowel (including bowel to viscera) as follows:

- 0 = no adhesion;
- 1 = minimal (<1/3 of the site is covered);
- 2 = moderate (1/3 to 2/3 of the site is covered), or
- 3 = extensive (>2/3 of the site is covered).

The severity of the adhesions in the region are graded using the following score:

- 0 = no adhesions;
- 1 = filmy thickness, avascular;
- 2 = moderate thickness, limited vascularity, or
- 3 = dense thickness, vascularized.

At the second surgery visit the site study staff will determine if the subject experienced a hospital readmission due to GI concerns and/or other medical reasons. If readmission did occur, this event should be recorded as a SAE.

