6.17. Appropriateness of Measurements

All procedures used to measure the safety and efficacy of LB1148 in this study are considered to be appropriate and necessary to obtain the required safety, tolerability, and efficacy data. The safety assessments used in this study, such as physical examination, vital signs, opioid use, laboratory assessments, and GI function assessments are widely used and are considered appropriate for monitoring subjects' health and well-being in this type of study. The measure used to evaluate pain levels is a validated and widely accepted rating scale used for clinical studies evaluating pain.

ADVERSE EVENTS ASSESSMENTS

AE data will be collected from first administration of study drug through Day 14, Hospital Discharge, or study termination, whichever comes first. Following discharge through the second surgery visit, any hospital readmissions will be recorded as SAEs.

AEs/SAEs related to the second surgery will also be collected.

Investigators are responsible for monitoring the safety of subjects who have entered this study and for alerting the Sponsor or its designees to any event that seems unusual, even if this event may be considered an unanticipated benefit to the subject.

The Investigator is responsible for the appropriate medical care of subjects during the study. The Investigator remains responsible for following, through an appropriate health care option, SAEs or AEs that caused the subject to discontinue before completing the study. The subject should be followed until the event is resolved or explained. Frequency of follow-up evaluation is left to the discretion of the Investigator.

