7.9. Adverse Event Reporting Period

AE data will be collected from first administration of study drug through Day 14, Hospital Discharge, or study termination, whichever comes first. Following discharge through the Month 3 visit, any hospital readmissions will be recorded as SAEs.

AEs/SAEs related to the second surgery will also be collected.

If a subject experiences an AE after signing informed consent, but prior to receiving study drug, the event will NOT be collected unless the Investigator feels the event may have been caused by a protocol procedure.

In addition, any known untoward event that occurs subsequent to the AE-reporting period that the Investigator assesses as related to the study drug should also be reported as an AE.

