7.13. Reporting Serious or Unexpected Adverse Events

Any SAE, irrespective of the relationship to study drug that occurs during the course of the study (from the first dose of study drug through Hospital Discharge, completion of Month 3 or early termination) will be reported on the eCRFs and SAE Report as soon as possible (within 24 hours after the site becomes aware of the event).

The Investigator is encouraged to discuss with the Sponsor's pharmacovigilance group any AE for which the issue of reportability is unclear or questioned.

An SAE Report should be prepared containing as much information as is available concerning the event so that a written report can be filed with appropriate regulatory authorities. If causality cannot be definitively assessed at the time of the SAE, it is important to notify Sponsor or its designees within the timelines stated above. When new significant information is obtained and the outcome and attribution of the event is known, the Investigator will communicate this information to the Sponsor or its designees and/or on the appropriate eCRFs. The relevant information will be provided in a timely manner to allow reporting to regulatory authorities within the required reporting period. Any SAE follow-up information requested by the Sponsor or its designees should be provided in a timely manner.

Additional information may be requested by the Sponsor or its designees to ensure that the initial reporting of SAEs is made to regulatory authorities within the requested timeframe. For a follow-up report to the regulatory authorities, the Sponsor or its designees may be required to collect further information for a detailed description and a final evaluation of the case, including copies of hospital reports, autopsy reports, or other relevant documents.

The Investigator, or Sponsor (or its designees) where applicable, will notify the relevant Institutional Review Board (IRB)/Independent Ethics Committee (IEC) of any SAEs and safety reports according to local regulation requirements.

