Appendix 1 Schedule of Assessments Protocol LBS-POI-201

Study Day	Screening	Surgical	Post-Surgical				Follow-Up	Second Surgery
	(-42 to -1 Days) ^{1,2}	Pre-Surgery / Surgery Day 0 ²	Post-Operative Days 1-6 ³	Post-Operative Day 7 ³	Post-Operative Days 8-14 ³	Hospital Discharge (Early Termination)	Day 30 (+7 Days)	Up to 8 Months after Day 0
Informed Consent	X							
Surgery Assessment		X						X
Study Eligibility Assessment ⁴	X	X ⁵						
Demographics & Medical History ⁵	X	X						
Concomitant Medication and Blood Products Review ^{5,6}	X	X	X	X	X	X		
Randomization ¹	X	X						
Taste Assessment		X						
Physical Exam ⁷	X	X	X	X	X	X		
Vital Signs ⁸	X	X	X	X	X	X		X
Study Drug Administration ^{2,9,10}	X	X						
Perioperative Surgical Preparation ¹¹	X	X						
Record Opioid Use	X	X	X	X	X	X		
Pain Assessment		X	X	X	X	X		X

Study Day	Screening	Surgical	Post-Surgical				Follow-Up	Second Surgery
	(-42 to -1 Days) ^{1,2}	Pre-Surgery / Surgery Day 0 ²	Post-Operative Days 1-6 ³	Post-Operative Day 7 ³	Post-Operative Days 8-14 ³	Hospital Discharge (Early Termination)	Day 30 (+7 Days)	Up to 8 Months after Day 0
GI Function Assessment								
Nausea			X	X	X	X		
Vomiting or Retching			X	X	X	X		
Flatus ¹²			X	X	X	X		
Stools ¹²			X	X	X	X		
NG/OG Tube			X	X	X	X		
Liquid Diet ¹²			X	X	X	X		
Solid Diet ¹²			X	X	X	X		
Adhesions Count		X						X
Hospital Discharge								
Hospital Discharge Order Written			X	X	X	X		
Hospital Departure			X	X	X	X		
Subject's Willingness To Discharge			X	X	X	X		
Adverse Events (AE)	X	X	X	X	X	X	X ¹³	X ¹⁴
Local Laboratory Tests¹⁵								
Urine or Serum Pregnancy Test ^{4,5}	X	X						
Labs (CBC, coagulation, and metabolic) ¹⁵	X		X	X				

Abbreviations: GI = gastrointestinal.

¹ Screening and Day 0 (Pre-Operative/Pre-Surgery) can be combined if the visit is on the day of first surgery. If this is the case, randomization will be performed during this study visit.

² Study Day 0 starts on the calendar day of the surgery; study dosing could occur Day -1 and/or up to 2 hours prior to surgery on Day 0.

³ Subject will be monitored from Screening through Post-Operative Days 14 until Hospital Discharge or Study Termination (whichever occurs first).

⁴ Eligibility assessment will include, if applicable, a negative pregnancy test.

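### Protocol 7.9 and 7.13 end post-discharge safety reporting at a Month 3 visit that is not in the schedule, while Section 7 and 6.16 run to the second surgery, leaving up to 5 months per subject under conflicting rules

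*Protocol*

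**What the plan says.** The protocol sets the end of post-discharge safety reporting in several places.

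- **Section 7, opening text:** "Following discharge through the second surgery visit, any hospital readmissions will be recorded as SAEs".
- **Section 7.9, Adverse Event Reporting Period:** the same sentence with a different end, "Following discharge through the Month 3 visit, any hospital readmissions will be recorded as SAEs". The section adds "AEs/SAEs related to the second surgery will also be collected" and asks for later events if the investigator considers them related to study drug.
- **Section 7.13:** the 24-hour duty covers any SAE whatever its relationship to study drug, "from the first dose of study drug through Hospital Discharge, completion of Month 3 or early termination".
- **Section 6.16:** "At the second surgery visit the site study staff will determine if the subject experienced a hospital readmission", and any readmission found is to be recorded as an SAE.
- **Appendix 1:** after hospital discharge there are two columns, a Day 30 (+7 days) contact and the second surgery, headed "Up to 8 Months after Day 0". There is no Month 3 column. Footnote 13 limits Day 30 recording to readmissions. Footnote 14 limits second-surgery recording to events related to the procedure.
- **Section 3.1:** "If a subject is not ready for the second surgery by 8 months, the investigator may consult with Medical Monitor to obtain window approval". No upper limit is given.

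**The concern.** One sentence appears twice in the same chapter with two different end points, and one of those end points is a visit that the trial no longer has. A site that works from 7.9 and 7.13 has grounds to treat its reporting duty as finished at three months. A site that works from the opening of Section 7 keeps recording readmissions until the second operation. Both would be following the protocol.

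Safety and tolerability is a secondary objective. Thrombotic events are of special interest (7.3, 7.4), and small bowel obstruction is one of the consequences of adhesions named in 1.3. The serious AE tables in SAP 12.1 would be fed by sites using different windows. The sponsor's blinded review of deaths and SAEs (10.6) depends on reports arriving promptly, and 7.13 is the section that sets the deadline.

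**Working it through.** The protocol states no figure to reproduce, so the check is a comparison of texts with one subtraction.

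**Step 1. Set the rules side by side for the period after discharge.**

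| Source | Events covered | Stated end |
|---|---|---|
| Section 7 opening | Readmissions, plus events related to the second surgery | Second surgery visit |
| 6.16 | Readmissions, asked about in retrospect | Second surgery visit |
| 7.9 | Readmissions | Month 3 visit |
| 7.9, further sentences | Events related to the second surgery; later drug-related events | No Month 3 limit |
| 7.13 | Any SAE, within 24 hours of awareness | Discharge, Month 3 or early termination, with no rule for which governs |
| Appendix 1, fn 13 | Readmissions | Day 30 contact |
| Appendix 1, fn 14 | Procedure-related events | Second surgery |

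The rows differ in end point (Month 3 against second surgery) and in scope (any SAE in 7.13, readmissions and surgery-related events elsewhere).

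**Step 2. Size the disputed window.** Let T be the month of the second surgery, counted from Day 0. The window is max(0, T − 3) months.

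- T = 3 or earlier: 0 months.
- T = 6: 6 − 3 = 3 months.
- T = 8, the scheduled maximum: 8 − 3 = 5 months, or 5/8 = 62.5% of the interval from Day 0 to surgery.
- T = 8 + x with Medical Monitor approval: 5 + x months, with x not bounded by the protocol.

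The documents give neither the distribution of T nor an SAE rate for this interval. The result is calendar time and cannot be turned into an expected number of missed events.

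**Step 3. Trace what happens to an event in the disputed window.**

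- *Readmission, subject reaches second surgery:* captured under 6.16 even at a site that follows 7.9, but possibly months later. On the wording of 7.13 it lies outside the 24-hour duty.
- *Readmission, subject never has the second surgery:* 6.16 is never triggered, and 7.9 has already ended. Only the opening of Section 7 could apply, and its end point never arrives.
- *SAE without readmission, judged drug-related:* still reportable under 7.9.
- *SAE related to the second surgery:* still collected under 7.9.
- *SAE without readmission, judged neither drug-related nor surgery-related (for example, a death outside hospital in month 5):* outside 7.13 after Month 3 and not clearly within the post-discharge sentence of Section 7 either.

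The last case shows that the Month 3 wording is only part of the problem. The difference in scope would leave it unsettled even if the dates agreed.

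**The case against.** The strongest reply is that this is leftover wording with little practical effect. Section 6.16 has no Month 3 limit and applies at every site, so an obstruction or thrombosis that leads to readmission in months 4 to 8 is picked up at the second operation. Section 7.10 then sends every SAE to the SAE Report. Section 7.4 asks for thrombotic events to be recorded without naming Month 3. As background only, the amendment log treats Month 3 as the second surgery when it describes the 7.13 wording. That suggests the intent was to follow subjects to that operation, and a site that finds no Month 3 visit may well look to the schedule. SAP 12.1 plans frequency tables, and the safety population already mixes follow-up lengths: subjects randomized before 01Jan2022 were complete at Day 30 with an optional second surgery (SAP 4.1), and they remain in that population. The readmission and obstruction objectives stop at 30 days, and the adhesion endpoint is untouched.

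Most of this stands. It rules out two stronger readings that a reader might infer. The first is that SAE reporting ceases at Month 3 and late SAEs are simply lost. Section 6.16 and the further sentences of 7.9 show otherwise. The second is that 62.5% measures lost safety data. It is the largest scheduled share of calendar time, for a month-8 surgery, and says nothing about the number of events.

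The reply does not remove the contradiction. A retrospective question at the second operation does not replace 24-hour reporting. It covers readmissions only, and it cannot reach a subject who dies, withdraws or never has the operation. Reliance on the investigator's judgement of causality after Month 3 also gives up what 7.13 was written to secure, which is reporting whatever the relationship. Intent inferred from a change log is not an instruction to sites.

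**Conclusion.** The current text of 7.9 and 7.13 contradicts the opening of Section 7 and Section 6.16, and it refers to a visit that is absent from Appendix 1. The conflict covers up to 5 months per subject at a month-8 surgery, more if the window is extended, and none if surgery takes place by Month 3.

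Three things are exposed: the 24-hour duty after Month 3; SAEs without readmission that are judged neither drug-related nor surgery-related; and readmissions in subjects with no second surgery. The number of affected events cannot be estimated from the documents. It is also not shown that any site has stopped reporting at Month 3; the point is that the protocol would permit it.

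The effect falls on safety oversight and the serious AE tables. It does not reach the adhesion endpoint or the 30-day objectives. The point assumes that sites apply the sections as written.

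**What to change.** Make two replacements in the next amendment: in 7.9, the second surgery visit in place of the Month 3 visit; in 7.13, completion of the second surgery visit in place of completion of Month 3.

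Those replacements align the dates but not the scope, so the same amendment should also:

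- choose one post-discharge scope, either all SAEs or readmissions plus surgery-related events, and state it identically in 6.16, 7, 7.9, 7.13 and Appendix 1 footnotes 13 and 14;
- add a rule to 7.13 saying which of its listed end points governs;
- define the end of reporting for subjects who have no second surgery and for those whose window is extended.

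Sites should then be asked to query enrolled subjects for unreported events after Month 3. For subjects still to have the second operation, this can be done at that visit, where staff already ask about readmissions.

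The cost is a short text change, a brief retrospective query and some additional SAE reports. No treatment, endpoint or sample size changes.

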7.10. Recording Adverse Events

All AEs will be documented in the appropriate section of the eCRFs. Among these AEs, all SAEs (refer to [Section 7.2](#)) will be additionally documented in the SAE Report.

The following will be recorded for each event in the eCRF:

- A description of the AE in medical terms, not as reported by the subject. Whenever possible, a diagnosis should be given when signs and symptoms are due to common etiology (e.g., cough, runny nose, sneezing, sore throat, and head congestion should be reported as “upper respiratory infection”).
- The date of onset (start date).
- The date of resolution (stop date).
- The severity as assessed by the Investigator according to the definitions in [Section 7.11](#).
- The causal relationship to study drug as assessed by the Investigator; the decisive factor in the documentation is the temporal relation between the AE and the study drug (refer to [Section 7.12](#)).
- Action taken for study drug (none, study drug discontinued, study drug dose reduction, study drug delayed).
- Other action(s) taken (none, concomitant medication given, new or prolonged hospitalization, procedural surgery).
- The outcome according to the following definitions:
 - Recovered with sequelae;
 - Recovered without sequelae;
 - Ongoing, no therapy;
 - Ongoing, therapy;
 - Died, and
 - Change in toxicity grade/severity.

- SAE (as defined in [Section 7.2](#)): Yes or No.

If, in any 1 subject, the same AE occurs on several occasions (unless the AE is continuous and of stable grade), then the AE in question will be documented and assessed each time. For an SAE, the information above recorded in the eCRF will also be recorded in the SAE Report. Only AEs that fulfill the criteria for SAEs (refer to [Section 7.2](#)) should be recorded in the SAE Report.

7.11. Assessing Adverse Event Severity

To ensure there is no confusion or misunderstanding of the difference between the terms “serious” and “severe”, which are not synonymous, the following note of clarification is provided:

The term “severe” is often used to describe the intensity (severity) of a specific event (as in mild, moderate, or severe myocardial infarction); the event itself, however, may be of relatively minor medical significance (such as severe headache). This is not the same as “serious”, which is based on subject/event outcome or action criteria usually associated with events that pose a threat to a subject’s life or functioning. Seriousness (not severity) serves as a guide for defining regulatory reporting obligations.

All AEs are to be evaluated with respect to severity using the National Cancer Institute (NCI) Common Terminology Criteria for Adverse Events (CTCAE) grading system ([Appendix 7](#)).

Grade refers to the severity of the AE. The CTCAE displays Grades 1 through 5 with unique clinical descriptions of severity for each AE based on this general guideline:

- Grade 1 Mild; asymptomatic or mild symptoms; clinical or diagnostic observations only; intervention not indicated.
- Grade 2 Moderate; minimal, local or noninvasive intervention indicated; limiting age-appropriate instrumental Activities of Daily Living (ADL). *Instrumental ADL refer to preparing meals, shopping for groceries or clothes, using the telephone, managing money, etc.*
- Grade 3 Severe or medically significant but not immediately life-threatening; hospitalization or prolongation of hospitalization indicated; disabling; limiting self-care ADL. *Self-care ADL refer to bathing, dressing and undressing, feeding self, using the toilet, taking medications, and not bedridden.*
- Grade 4 Life-threatening consequences; urgent intervention indicated.
- Grade 5 Death related to AE.

7.12. Assessing Adverse Event Relationship to Study Drug

The Investigator must record his/her opinion concerning the relationship of the AE to study therapy on the eCRF. Investigators will determine relatedness of an event to study drug based on

a temporal relationship as well as if the event is unanticipated or unexplained given the subject's clinical course, previous medical conditions, and concomitant medications. An event should be recorded as "drug related" if the Investigator believes it to be reasonably related to study drug.

